8.5 Study Population with inclusion and exclusion criteria

Five non-mutually exclusive study cohorts for the analyses will be defined:

- 1. General population cohort for pre-pandemic background rates** will have
 - Individuals will start contributing as of 1st January 2017, or when they have at least 365 days of data availability.
 - follow-up for this cohort will run up to 31 December 2019.
- 2. Persons tested positive for SARS-CoV-2 or with a clinical diagnosis of COVID-19 during the Omicron period** will
 - have either a positive test result for SARS-CoV-2 or a clinical diagnosis of COVID-19 on or after 1st December 2021 (with the index date being whichever date comes first if both occur)
 - have no positive test result for SARS-CoV-2 or clinical diagnosis of COVID-19 within 3 months prior to the index date.
 - have at least 365 days of data availability prior to index date
- 3. Persons hospitalised with COVID-19 during the Omicron period** will have
 - a hospitalisation on or after 1st December 2021 (with the index date the date of hospital admission),
 - a record of a clinical diagnosis of COVID-19 or a positive test result for SARS-CoV-2 in the period between 3 weeks prior to and up to 3 days following the index date.
 - have no diagnosis of COVID-19 or a positive test result for SARS-CoV-2 between 3 months and 3 weeks prior to index date.
 - have no COVID-19 hospitalisation within 3 weeks prior to the index date.
 - have at least 365 days of data availability prior to index date
- 4. Persons requiring intensive services during a hospitalisation with COVID-19 during the Omicron period** will have
 - intensive services initiated during a hospitalisation as described in cohort 3 (with the index date the date at which intensive services were initiated)
 - patients will have had a confirmatory diagnosis or test result of COVID-19 (both as defined above) within a time window from 3 weeks to their index date up to three days following their index date.
 - have at least 365 days of data availability prior to index date
- 5. Persons vaccinated against SARS-CoV2 infection**
 - a vaccination record identified by brand (with the index date the date of vaccination record)
 - whether the vaccination record is 1st, 2nd, 3rd or 4th dose. A 21 day gap between two consecutive records of vaccine will be required to avoid repeated records of the same vaccine. The 21-days period was chosen based on the minimal recommended dosing schedule of the primary vaccine course in participated databases (Spain).
 - have at least 365 days of data availability prior to index date

Cohorts 2 to 5 will be stratified by prior COVID-19 infection status and for cohorts 2 to 4 also by prior SARS-CoV-2 vaccination status. All cohorts will additionally be stratified by whether patients are immunocompromised on the index date. People in each of the five cohorts will be required to have at least a year of observed history in the database prior to their index date. This is to ensure a sufficient time period to identify health conditions and medication use prior to individuals' index dates.

	Phase II C3-001 – Study Protocol	
	Author(s): [name], [name]	Version: v3.1
		Dissemination level: public

Table 3. Operational Definitions of Inclusion Criteria

Criterion	Details	Order of application	Assessment window	Care Setting ¹	Code Type	Diagnosis position ²	Applied to study populations:	Measurement characteristics/validation	Source for algorithm
Observation period of 365day prior entry (all 5 cohorts)	Study participants will be required to have 365 days prior history observed before contributing observation time	before	[-365,0]	n/a	n/a	n/a	All individuals within the selected databases	n/a	n/a
Covid-19 infection (cohort 2)	have either a positive test result for SARS-CoV-2 or a clinical diagnosis of COVID-19 on or after 1 st December 2021 (with the index date being whichever date comes first if both occur)	before	n/a	Primary care	SNOMED	n/a	All individuals within the selected databases	n/a	n/a
Covid-19 hospitalized (cohort 3)	a hospitalisation on or after 1 st December 2021 (with the index date the date of hospital admission), a record of a clinical diagnosis of COVID-19 or a positive test result for SARS-CoV-2 in the period between 3 weeks prior to and up to 3 days following the index date	before	[-21, 3]	Primary care, secondary care	SNOMED	n/a	All individuals within the selected databases	n/a	n/a

	Phase II C3-001 – Study Protocol	
	Author(s): [name], [name]	Version: v3.1
	Dissemination level: public	

Covid-19 intensive care use (cohort 4)	intensive services initiated during a hospitalisation as described in the “covid-19 hospitalized” criterion	before	During hospitalization	Intensive care	SNOMED	n/a	Individuals who met the “covid-19 hospitalized” criteria	n/a	n/a
Covid-19 vaccinated (cohort 5)	a vaccination record identified by brand (with the index date the date of vaccination record)	before	n/a	Primary care	RxNorm	n/a	All individuals within the selected databases	n/a	n/a

¹ IP = inpatient, OP = outpatient, ED = emergency department, OT = other, n/a = not applicable

² Specify whether a diagnosis code is required to be in the primary position (main reason for encounter)

Table 4. Operational Definitions of Exclusion Criteria

Criterion	Details	Order of application	Assessment window	Care Setting¹	Code Type	Diagnosis position²	Applied to study population^s	Measurement characteristic^{s/}	Source for algorithm
Prior covid-19 (cohort 2-4)	have no positive test result for SARS-CoV-2 or clinical diagnosis of COVID-19 within 3 months prior to the index date.	After	[-91,0]	OP,IP	SNOMED, RxNorm	n/a	SARS-CoV-2 infected, hospitalized (cohorts 2, 3, 4)	n/a	n/a

	Phase II C3-001 – Study Protocol	
	Author(s): [name], [name]	Version: v3.1
	Dissemination level: public	

Hospitalization (cohort 3)	have no diagnosis of COVID-19 or a positive test result for SARS-CoV-2 between 3 months and 3 weeks prior to index date. Have no COVID-19 hospitalisation within 3 weeks prior to the index date.	After	Covid-19 [-91,-21]; Hospitalization [-21,0]	IP	SNOMED	n/a	Covid-19 hospitalized (cohorts 3, 4)	n/a	n/a
Vaccinated (cohort 5)	No vaccine records in the 21 days prior to index vaccine	after	[-21 , 0]	OP	RxNorm	n/a	Vaccinated (cohort 5)	n/a	n/a
Prior outcomes all cohorts)	Exclude people with the outcome of interests during the 183 day prior to index. (primary analysis, different washout period will be applied in sensitivity analysis)		[-183,0]	IP, OP	SNOMED	n/a	(cohorts 1-5)	n/a	n/a

1 IP = inpatient, OP = outpatient, ED = emergency department, OT = other, n/a = not applicable

2 Specify whether a diagnosis code is required to be in the primary position (main reason for encounter)

Criterion: A brief text entry naming the in- and/or exclusion criterion (e.g. age, sex, atrial fibrillation)

Details: An optional brief text description to provide more information about the in- and/or exclusion criterion (e.g. age in years defined by (time 0 – year of birth)/365, baseline enrolment measured by Part A, B, D and no HMO insurance coverage with 30 day gaps allowed), 2 codes required

	Phase II C3-001 – Study Protocol	
	Author(s): [name], [name]	Version: v3.1
		Dissemination level: public

Order of application: Specify whether the in and exclusion criterion is applied before or after selection of the study entry date. For example, enter “before” if you plan to apply the criterion, identify all possible study entry dates, and then choose one or more. Enter “after” if you select the first possible study entry date and then apply the in- and/or exclusion criterion. If the patient does not meet the criterion, then the patient drops out. These decisions can impact which samples of person-time are included in the study.

Assessment window: Use bracketed numbers representing time intervals anchored on a primary anchor (usually time 0) to specify the window over which to evaluate patient data relevant for the in- and/or exclusion criterion. For example, [-180, 0] would reflect an assessment window of 180 days prior to and including time 0, where the brackets indicate that the window is inclusive of the endpoints.

Care setting: Specify the care setting(s) that are used in the algorithm to define the in- and/or exclusion criterion. For example, IP = inpatient, ED = emergency department, etc.

Code type: Specify the type(s) of clinical codes that are used to define the in- and/or exclusion criterion.

Diagnosis position: If the algorithm to define the in- and/or exclusion criterion used inpatient codes, specify whether the algorithm restricts to primary diagnosis codes (indicating that the code is the primary reason for the encounter) or allows codes in secondary or any position (e.g. primary, secondary, any, n/a)

Applied to study populations: Indicate which study populations the in- and/or exclusion criterion should be applied to (study population names are specified in Table 2).

Measurement characteristics/validation: If there are measurement characteristics for the outcome algorithm (e.g. PPV, sensitivity, specificity) from publications, or from outcome validation within the study population (e.g., medical record review), provide this information.

Source of algorithm: Specify the source of algorithms to define the in- and/or exclusion criterion.

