3. ABSTRACT (STAND ALONE SUMMARY OF THE STUDY PROTOCOL)

Title: DARWIN EU – EHDS Use Case: Natural history of coagulopathy in COVID-19 patients and persons vaccinated against SARS-CoV-2 IN the context of the OMICRON variant

Rationale and background: Coronavirus disease-2019 (COVID-19) patients are at increased risk of venous and arterial thromboembolic events. SARS-CoV-2 variants have evolved during the COVID-19 pandemic with the dominant variant being Omicron now (as of December 2021). Information relating to thromboembolic risk and its impact on COVID-19 largely relates to COVID-19 variants occurring earlier during the pandemic. Therefore, evidence used to contextualize coagulopathy risk in light of vaccination may now differ. There is a need to better understand the risks of thromboembolic events among patients with COVID-19 associated with the Omicron variant, their impact on prognosis, and whether risk factors for such events remain the same, overall and in the context of prior COVID-19 infection, SARS-CoV-2 vaccination and among certain subgroups.

This study is one of the five use cases selected in the pilot project to test and inform HealthData@EU frameworks. HealthData@EU pilot project is the European Health Data Space (EHDS) Pilot project that aims to investigate and establish an infrastructure and data ecosystem for the secondary use of health data to facilitate research, innovation and better policy making; and assess the ability to scale towards a Union-wide infrastructure, as a core component of the EHDS.

Objectives:

1. To estimate the background incidence rate of venous and arterial thromboembolic events among the general population pre-pandemic population.
2. To estimate the incidence rate of venous and arterial thromboembolic events among patients with COVID-19 within 30-, 60-, 90- and 180-days during the Omicron period, stratified by prior SARS-CoV-2 vaccination and prior infection status.
3. To estimate the incidence rate of venous and arterial thromboembolic events among patients with SARS-CoV-2 vaccination within 30-, 60-, 90- and 180-days, stratified by prior infection status.
4. To estimate a) the association between clinical risk factors and prior SARS-CoV-2 vaccination on the incidence rate of venous and arterial events among people with COVID-19 and b) the impact that thromboembolic events have on worsening severity of COVID-19 during the Omicron period.

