5. To estimate incidence rate ratios for venous and arterial thromboembolic events among patients with COVID-19 and different SARS-CoV-2 vaccine doses compared to the background population, using incidence rates estimated in objectives 1 to 3.

Study type: population-level cohort

Study population:

- 1) Pre-pandemic cohort to calculate background rates of venous and arterial thromboembolic events in the general population (year 2017-2019).
- 2) People with COVID-19 during the time when OMICRON was the dominant variant (coded or test positive). All participants are required to be visible in the data source since 1st January 2020 to have full records on infection and vaccination history.
- 3) People vaccinated against SARS-CoV-2 (+/- during the period when OMICRON was the dominant variant). All participants are required to be visible in the data source since 1st January 2020 to have full records on infection and vaccination history.

For all cohorts, individuals with recent VTE or ATE event (defined as having a diagnosis of VTE or ATE within 183 days prior to index date, with sensitivity analysis of using any time prior and 91-days as wash-out periods.) will be excluded.

	Phase II C3-001 – Study Protocol	
	Author(s): [name], [name]	Version: v3.1
		Dissemination level: public

Analysis:

Standardized incidence rate ratio (SIR) compared to the background population will be estimated using indirect standardization.

Cohorts will be stratified by prior COVID-19 infection occurrence and prior SARS-CoV-2 vaccination (COVID-19 and vaccine cohorts only), age, sex. All cohorts will additionally be stratified by whether patients are immunocompromised on the index date.

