Studies assessing the incidence of thromboembolic events among people with COVID-19 during the early period of the pandemic were conducted in relatively small study populations, partly constrained by data availability at the time, and predominantly focused on hospitalised populations. Consequently, uncertainty remained around the incidence of thromboembolic events among patients with COVID-19. Several larger studies examining coagulopathy risk have since been conducted using routinely collected health data. One study from Sweden demonstrated an increased risk of deep vein thrombosis (DVT) up to 70 days post-COVID-19 diagnosis and an increased risk of pulmonary embolism up to 110 days post-COVID-19 diagnosis.[5] Meanwhile, another study from England reported an increased risk of venous thromboembolism up to 49 weeks post-COVID-19.[6] Studies have also observed that the elevated risk of thromboembolic events associated with COVID-19 infection may be attenuated following SARS-CoV-2 vaccination.[7] SARS-CoV-2 variants have changed over time, with Omicron now widely established as the dominant SARS-CoV-2 variant. On 26 November 2021, the European Centre for Disease Prevention and Control classified the Omicron B.1.1.529 variant as a variant of concern due to concerns regarding immune escape and potentially increased transmissibility compared to the SARS-CoV-2 delta variant.[8] However, existing studies largely examined COVID-19 during the period when Omicron was not the dominant variant. The risk of venous and arterial thromboembolic events with Omicron COVID-19 is therefore less well studied, particularly in the context of exposure to either prior COVID-19 infection or prior SARS-CoV-2 vaccinations.

Thromboembolic events and worsening of COVID-19 during the Omicron period

COVID-19 patients with thromboembolic events are at increased risk of worse outcomes, with a systematic review finding a strong association between cardiovascular and thromboembolic events and poor prognosis among people with COVID-19.[9] However, it has been suggested that the Omicron variant has a milder course and therefore, subsequent coagulopathy risk may differ. This may be further influenced by prior SARS-CoV-2 vaccination. As with measuring the incidence of thromboembolic events themselves, routinely collected data may also be used to describe the risks of worsening among people with COVID-19 during the period when Omicron was the dominant variant.

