8.3 Study Period

The study period will start depending upon when the Omicron variant became established in Europe commencing from 1st December 2021.[8] The end of the study period will be the last available date of data collection for each contributing dataset.

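### Cohorts 3 and 4 apply the 1 December 2021 Omicron start to the hospital admission and not to the infection record, so infections recorded from 10 November can count as Omicron

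*Protocol*

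**What the plan says.** Calendar date is the only criterion that makes a case an Omicron case, and section 8.5 of the protocol attaches it to different events.

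- **Cohort 2** (infected): people must "have either a positive test result for SARS-CoV-2 or a clinical diagnosis of COVID-19 on or after 1st December 2021". The floor is on the test or diagnosis.
- **Cohort 3** (hospitalised): people must have "a hospitalisation on or after 1st December 2021 (with the index date the date of hospital admission", together with "a record of a clinical diagnosis of COVID-19 or a positive test result for SARS-CoV-2 in the period between 3 weeks prior to" that admission, or up to 3 days after it. Table 3 gives this window as [-21,3], and section 8.6.1 and Table 5 repeat it. None of them sets a calendar floor on the COVID-19 record.
- **Cohort 4** (intensive services): the services must begin during a cohort 3 hospitalisation, and the COVID-19 record must also lie between 3 weeks before and 3 days after the start of those services.

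On the Omicron period itself, section 8.3 states: "The study period will start depending upon when the Omicron variant became established in Europe commencing from 1st December 2021". Section 6 gives the earlier landmark: "On 26 November 2021, the European Centre for Disease Prevention and Control classified the Omicron B.1.1.529 variant as a variant of concern". The abstract describes the population differently, as "People with COVID-19 during the time when OMICRON was the dominant variant", and supports dominance only with the remark "with the dominant variant being Omicron now (as of December 2021".

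Table 4 has two rows that bear on the window. One excludes prior COVID-19 over [-91,0] and lists cohorts 2, 3 and 4. The other, for cohorts 3 and 4, excludes it over [-91,-21].

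**The concern.** The study asks whether thromboembolic risk seen with earlier variants carries over to Omicron, which section 6 says may run a milder course. For that question the infection date matters, because the variant is fixed at infection and not at admission. A floor on admission combined with a 21-day look-back lets infections recorded before the declared Omicron period into the Omicron hospital and intensive-care cohorts.

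These cohorts feed the incidence estimates (section 8.8.2), the risk-factor Cox models, which are run for each COVID-19 cohort (section 8.8.3), and the comparison with background rates (section 8.8.5). If earlier variants carried higher risk, the affected estimates would move towards the earlier-variant values from which the study wants to distinguish them. Table 9 varies the test type, the source of cardiovascular events and the outcome washout, but not the start date. Section 11 does not mention misclassification by variant.

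**Working it through.** The protocol states no figure to reproduce. The check is calendar arithmetic on its own dates.

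**Inputs**
- Omicron start: 1 December 2021 (section 8.3).
- Variant-of-concern classification: 26 November 2021 (section 6).
- Window for the qualifying COVID-19 record in cohort 3: day -21 to day +3 around admission (section 8.5, Table 3).
- Only database with inpatient data: SIDIAP (section 7, Setting row), listed lock 1/6/2022 (Table 1). This is read as 1 June 2022, since another lock in the same table, 31/3/2021, shows day before month.

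**Earliest qualifying infection record in cohort 3**
- 1 December − 21 days = 10 November 2021.
- Distance to the Omicron start: 21 days. Distance to the classification: 26 − 10 = 16 days.
- If the closed [-91,-21] exclusion removes day -21, the earliest date is 11 November, 15 days before the classification.

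**Admissions that can be affected**
- Last admission that can rest on a record before 1 December: 30 November + 21 days = 21 December.
- Last admission that can rest on a record before 26 November: 25 November + 21 days = 16 December.
- Days from 1 December 2021 to 1 June 2022: 31 + 31 + 28 + 31 + 30 + 31 = 182.
- Share of accrual days: 21/182 = 11.5%, and 16/182 = 8.8%. These are shares of calendar days, not of patients. Only some admissions on those days will have an older record.

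**Cohort 4**
- The record must also lie within 21 days before intensive services start. A record of 10 November therefore qualifies only if both admission and intensive services fall on 1 December. A record of 30 November qualifies if services start by 21 December.

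**One infection, two answers**
- Diagnosis 20 November, admission 2 December: the gap is 12 days, inside [-21,3] and outside [-91,-21]. Cohort 3 admits the case.
- Cohort 2 rejects it, because the diagnosis precedes 1 December. A repeat positive test in December would not help, because of the 3-month rule on earlier COVID-19 records.

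**Does Table 4 already close the gap?**
- Read literally, the [-91,0] row would remove every COVID-19 record up to and including the admission day. Cohort 3 would keep only records from days 1 to 3 after admission, so the earliest record would be 2 December.
- The same row applies to cohort 2, where day 0 is the index infection, and would exclude every member. It also defeats the purpose that section 8.6.1 gives for the window, which is to take in diagnoses made before admission. It cannot operate as written.

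**Weight of early admissions in long follow-up**
- A patient admitted on 22 December reaches day 182 − 21 = 161 at the listed lock. All cohort 3 person-time beyond day 161 therefore comes from the admissions of 1 to 21 December, whether or not each rests on an older record.
- A full 180 days is reachable only for admissions up to 3 December (182 − 180 = 2 days after 1 December).

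**The case against.** The strongest reply is that the problem is narrow. It is confined to SIDIAP and to three weeks of admissions. The earliest date is reached only by an admission on exactly 1 December with a record at exactly day -21. The look-back was chosen on purpose, to include people diagnosed before admission. The population given for objective 2 in section 7 is cohort 2, where the floor is on the infection itself. The multistate model for worsening (section 8.8.4) starts from an outpatient test or diagnosis, so if people enter it through cohort 2, the look-back does not reach it. All of this stands and limits the size of the point. It does not remove the inconsistency, because a look-back can be kept while a calendar floor is placed on the record.

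Two stronger readings are tempting, and the documents do not support them.

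- **That earlier-variant cases demonstrably enter cohort 2**, because it opens five days after the classification. The protocol gives no variant shares by week or country. A variant-of-concern classification is not a statement about share, and the surveillance source cited for the start date is not available here. Such cases are a plausible inference of unknown size.
- **That the bias can be quantified.** One could write the inflation as 1 + s × d × (r − 1), with s the share of early cases, d the fraction of those from earlier variants and r the risk ratio per case. The documents supply none of the three. Assumed values of 0.10, 0.3 and 1.5 give +1.5%, and 0.30, 0.7 and 3 give +42%, so the answer is set by the assumptions.

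**Conclusion.** The point holds for cohorts 3 and 4 on the protocol's text alone. As written, the plan labels as Omicron some hospitalised cases whose infection was recorded before its own Omicron period, and treats the same infection differently in cohort 2. The reach is records from 10 or 11 to 30 November 2021, through SIDIAP admissions of 1 to 21 December, which are 11.5% of accrual days to the listed lock. This rests on two assumptions: that section 8.5 and Table 3 govern over the unworkable [-91,0] row, and that the lock is not moved before execution. A later lock would dilute the share. The number of patients affected and the change in any rate or ratio cannot be derived.

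For cohort 2 the finding is limited to a mismatch of terms. The start is justified by Omicron being *established*, while the population is described as infected when it was *dominant*, and no analysis tests whether the difference matters. The remedy is cheap and the point is worth correcting before the code is run, but it does not threaten the study as a whole.

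**What to change.** 1. In section 8.5 and Table 3, require the qualifying COVID-19 record in cohorts 3 and 4 to be dated on or after 1 December 2021, matching cohort 2. The earliest infection record then moves from 10 November to 1 December.
2. In Table 4, reconcile the [-91,0] and [-91,-21] rows with the [-21,3] inclusion window, so that no day is both required and excluded and the index infection is not removed.
3. In Table 9, add one sensitivity analysis for cohorts 2 to 4 with a modestly later start, or a country-specific start based on Omicron dominance with its source stated. Keep 1 December as primary.

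The cost is one date filter, a table correction and one rerun. Some early-December admissions are lost, and those kept from the first days have short gaps between diagnosis and admission, which may make them a particular group. The later-start run has shorter follow-up. At the listed SIDIAP lock, no one indexed after 3 December can complete 180 days, so in that database the run should be read mainly at 30 to 90 days. The start should not be moved far: 1 February 2022, for example, would leave at most 28 + 31 + 30 + 31 = 120 days.

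### The vaccinated cohort has no recent-COVID-19 exclusion and no recency split of prior infection, so VTE risk left over from a recent infection inflates the prior-infection vaccine SIR and, less so, the overall one

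*Protocol*

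**What the plan says.** Under the protocol's section 8.5, a person enters cohort 5 with "a vaccination record identified by brand (with the index date the date of vaccination record") plus a dose number, a 21-day gap from other vaccine records and 365 days of history. The only cohort-specific exclusion in Table 4 is "No vaccine records in the 21 days prior to index vaccine". Table 4 also removes anyone, in any cohort, with the outcome in the 183 days before index.

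The COVID-19 washout is a different row of Table 4. It requires that people "have no positive test result for SARS-CoV-2 or clinical diagnosis of COVID-19 within 3 months prior to the index date", with window [-91,0], and its population column reads "SARS-CoV-2 infected, hospitalized (cohorts 2, 3, 4"). Cohort 5 is not listed.

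Infection history reaches cohort 5 only as a stratifier: "Cohorts 2 to 5 will be stratified by prior COVID-19 infection status". The abstract words this as "Cohorts will be stratified by prior COVID-19 infection occurrence and prior SARS-CoV-2 vaccination (COVID-19 and vaccine cohorts only), age, sex", and section 8.8.5 calls it prior COVID-19 diagnosis. None of these attaches a time window. The abstract also states "All participants are required to be visible in the data source since 1st January 2020 to have full records on infection and vaccination history", so the look-back runs to January 2020.

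Section 6 cites a Swedish study reporting "an increased risk of deep vein thrombosis (DVT) up to 70 days post-COVID-19 diagnosis and an increased risk of pulmonary embolism up to 110 days" after diagnosis, and then an English study reporting raised VTE risk up to 49 weeks.

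**The concern.** A person infected 20 days before a dose and a person infected 18 months before it fall in the same prior-infection stratum. On the protocol's own background, the first still has 90 days of raised PE risk to run (110 - 20) and 50 days of raised DVT risk (70 - 20). All of that time falls in vaccine follow-up, which lasts 30 to 180 days from the dose. A VTE due to the infection is then counted as an observed event after vaccination.

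Section 8.8.5 reports the vaccine SIR both overall and by prior COVID-19 diagnosis, against a 2017-2019 background and standardised for age and sex only. Both outputs would be raised even if the vaccine did nothing. Section 6 says earlier SIRs were raised far more after infection than after vaccination, so the contamination runs from the stronger exposure into the weaker one. Objective 5 places both sets of SIRs against the same background, and its hypothesis is that infection or vaccination may change event rates. A reader will compare them.

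**Working it through.** The protocol states no SIR or share that could be reproduced, so the check has two parts: whether any rule removes the carried-over risk, and how large it could be under stated assumptions.

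**Rules that might remove it**

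- Table 4, COVID-19 washout: covers cohorts 2 to 4 only.
- Table 4, 183-day outcome exclusion: removes events before the dose, not later events caused by the earlier infection.
- Section 8.4, end of follow-up: acts after entry, whereas the infection precedes entry.
- Section 8.8.5, standardisation: age and sex only.
- Section 8.6.3, hospitalised on the index date: isolates people in hospital on the day of the dose, not recent outpatient infections. Inpatient data exist only in SIDIAP.
- Table 9, sensitivity analyses: vary test type, inpatient recording and outcome washout, not infection before a dose.
- Section 8.8.5, stratum without prior COVID-19 diagnosis: free of recorded recent infection. This does protect that stratum, but not the other two outputs.

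**Size in the prior-infection stratum**

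Assumptions, none of which is given in the document:

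- The vaccine has no effect.
- A share f of the stratum (strictly, of its expected events) was infected in the 110 days before the dose, evenly spread.
- The rate is R times background until day 110 after infection and equals background afterwards.
- Earlier infections carry no excess.

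The remaining risk time at the dose is uniform on 0 to 110 days. For a window of T days, the fraction p of follow-up inside the risk period is:

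- T ≤ 110: p = 1 - T/220
- T = 180: p = 55/180, since the mean remaining time is 55 days

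The expected SIR is 1 + f(R - 1)p.

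| Window | p | f = 10%, R = 1.5 | f = 20%, R = 2 | f = 40%, R = 3 |
|---|---|---|---|---|
| 30 days | 1 - 30/220 = 0.86 | 1.04 | 1.17 | 1.69 |
| 60 days | 1 - 60/220 = 0.73 | 1.04 | 1.15 | 1.58 |
| 90 days | 1 - 90/220 = 0.59 | 1.03 | 1.12 | 1.47 |
| 180 days | 55/180 = 0.31 | 1.02 | 1.06 | 1.24 |

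For example, at 30 days the top value is 1 + 0.40 × 2 × 0.864 = 1.69.

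With the 70-day DVT limit instead, and infection still spread over 110 days, the mean remaining time is (70²/2)/110 = 22.3 days. At 180 days p = 22.3/180 = 0.12, and the top value falls to 1 + 0.8 × 0.12 = 1.10.

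**Size in the overall SIR**

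The same formula applies with f as the share of all doses. At 30 days and R = 2, f = 1% gives 1 + 0.01 × 0.864 = 1.01, and f = 5% gives 1.04.

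**Would it be visible?**

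An approximate 95% interval excludes 1 once expected events reach 1.96² × SIR/(SIR - 1)². That is 116 events for an SIR of 1.20 and 423 for 1.10. In strata of that size, a bias of this order could be read as a finding.

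**The case against.** Several points on the other side stand. The stratum without prior infection is already a planned output, contains no recorded recent infection, and can be set beside the other stratum. The share of doses given soon after COVID-19 is unknown and may be low, which would make the overall effect negligible. Section 6 notes that most evidence is pre-Omicron and that the raised risk may be attenuated after vaccination, so for later doses R may lie at the low end or below it. The durations in section 6 concern DVT, PE and VTE; none is given for arterial events, the other primary outcome.

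It can also be said that the levels of a stratifier are often fixed in a statistical analysis plan, and that no yes/no coding is printed. That is true of the coding. The scope of the exclusion, however, is settled in Table 4, and no wording of the stratifier anywhere suggests recency.

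A reader might infer more than the document supports:

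- That the vaccine SIRs as a whole are invalid. They are not, because the no-prior-infection stratum stands.
- That the null SIR could be 1.8 (1 + 0.4 × 2) in every window. That applies the excess to the whole of follow-up; on the protocol's own 110 days the same inputs give 1.69 at 30 days and 1.24 at 180 days.
- That the study exists to separate the two exposures. Its stated aim is to contextualise risk, objectives 1 to 3 are labelled descriptive, and the cohorts are declared non-mutually exclusive.
- That a headline SIR is compromised. The protocol designates none.

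**Conclusion.** The point holds for VTE in two planned outputs: the prior-infection vaccine SIR and, to a smaller and unknown degree, the overall vaccine SIR. The bias is upward whenever some doses follow a recent infection and that infection still carries excess risk. It is greatest in the 30- to 90-day windows. Under the assumptions shown, the null SIR in the prior-infection stratum is about 1.04 to 1.69 at 30 days, 1.03 to 1.47 at 90 days and 1.02 to 1.24 at 180 days. Both the share and the rate ratio are assumed, so these figures illustrate the possible size and do not estimate it. If the 49-week figure applied, earlier infections would add to the excess. This is an inexpensive improvement worth making before the code is run; it is not a flaw that undermines the study.

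**What to change.** In cohort 5, classify prior infection at each dose as none, recent or earlier. Define recent by the 91-day window already applied to cohorts 2 to 4 or by the 110 days cited in section 6, and fix the choice in advance. With 91 days, infections from day 91 to day 110 would still bring at most 19 days of the cited PE risk into follow-up.

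Report the recent group separately. Add to Table 9 a sensitivity analysis of the overall dose- and brand-specific SIRs that excludes people with a recorded recent infection. State in section 11 that some excess may remain beyond either cut, given the cited 49 weeks.

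The infection dates are already needed for the planned stratification, so the work is one three-level variable and one filter. The price is smaller prior-infection cells, some of which may have 5 events or fewer and so miss the Table 8 reporting threshold for rates within age-sex strata, plus some lost person-time in the sensitivity analysis. The document does not allow either loss to be quantified.
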